### The following criteria must be met for subjects to be randomized into the study:

- 1) T2DM with suboptimal glucose control (A1C  $\geq 6.5\%$ ),
- 2) AHI greater than  $\geq 10$  (ApneaLinkPlus®),

- 3) Age 18 years or older
- 4) Willing to be randomized to CPAP or sham-CPAP.

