#### **Procedures**

**Assessment 1.** Written and verbal explanation of the purpose, protocol, risks and benefits of the study will be provided and informed written consent will be obtained. The subject's ability to read at the 5th grade reading level and comprehend information will be evaluated with questions that ask “if you feel sleepy, should you drive a car or use dangerous machines?” Health literacy will be evaluated by the Newest Vital Sign. A urine pregnancy test will be done, if appropriate. Study staff will perform anthropometric measurements (height, weight, body composition) and a

venipuncture to obtain no more than 30 cc blood for A1C, fructosamine, and lipid profile. Waist circumference will be measured twice with an inelastic measuring tape. The Project Manager/ Study Coordinator will instruct subjects on how to wear the ApneaLinkPlus® device that night when they go to sleep. Subjects' will be instructed on wearing the SenseWear Armband® and filling out the Sleep/Activity/Diet Diary when they wake up and before bedtime for the next 7 days. Subjects will be instructed how to complete the questionnaires at home during the next week. They will be given two padded pre-paid mail packets: the first for returning the ApneaLinkPlus® the next day and the second to return the SenseWear Armband, questionnaires, and the Sleep/Activity /Diet Diary after using them for 7 days. Data from the ApneaLinkPlus® will be uploaded and data reviewed by either Drs. [name] or [name] (at Pitt/VAPHS) or [name] (at WVU) to determine the AHI. When the ApneaLinkPlus® is uploaded, if there is inadequate data to determine AHI eligibility, we will contact the participant and ask if they would be willing to repeat the ApneaLinkPlus® at home sleep study.

History and Physical. Subjects will have a history & physical by a Nurse Practitioner or Medical Fellow to determine if there is any factor that may exclude them from the study. Drs. [name], [name] or [name] will determine if subjects meet all study criteria for randomization.

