Diabetes Education/Counseling. The DEC will consist of two (2) one-on-one sessions (a 90 minute session and a 60 minute session), and a minimum of 3 follow-up phone calls of approximately 15-30 minutes with a diabetes educator that will start approximately one week after subjects have started CPAP or sham-CPAP. (see Appendix for Curriculum). Subject education will be provided using published educational materials from the American Diabetes Association and the American Association of Diabetes Educators. Partners will be encouraged to attend the sessions. Data from a RCT suggests that 3 1-hr individual sessions results in significantly (p-values  $<.05$ ) decreased A1C and stress associated with diabetes management compared to 8-hrs of group sessions. Although the content will be interactive and tailored to match each individual's needs and cultural influences, all subjects will receive standardized DEC based on the AADE patient competencies (AADE7). Subjects will be provided a pedometer to wear each day and a daily goal of steps, which will be increased over the 12 weeks to reach at least 7,500 steps per day. They will be given 7-day paper diaries and asked to record their daily food and beverage intake, physical activity and sleep habits. The diabetes educator will review the diaries at each of the two intervention sessions; will provide written and oral feedback on progress made toward improving their eating and physical activity habits. Subjects will be instructed on the value of self-monitoring diet and exercise to monitor progress to their behavior change goals. Subjects will be questioned on sleepiness before and after the session with the Stanford Sleepiness Scale. Vigilance will be tested before and after each DEC session with the

PVT-B. (Clarification in protocol 7.25.2018): The Stanford Sleepiness Scale is a part of the PVT-B Vigilance test. The West Virginia University site does not perform the PVT-B testing.

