Analysis Strategy for Aim 4. For this aim we will combine the 6 months of data for the two groups receiving CPAP (including the participants in the delayed treatment group who crossover to CPAP) to *explore* retention of treatment effects and to explore the association between the durability of treatment of OSA (i.e. adherence to CPAP) and 1) sleep

quality [PSQI], 2) daytime sleepiness [ESS], 3) mood [POMS], 4) diabetes self-management [SDSA, DES-SF, PAID7, and 5) glycemic control [fructosamine and A1C] after 24 weeks of active CPAP. For delayed treatment group participants, the initial assessment for this analysis will be their assessments at 12 weeks from study start. Random coefficient modeling will be applied to model changes in sleep quality, daytime sleepiness, mood, diabetes self-management and glycemic control and to associate these changes with objectively measured CPAP adherence via the EncoreAnywhereTM. Estimated regression coefficients and confidence intervals will be reported to summarize changes in outcomes over time and their associations with CPAP adherence.

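### Aim 4 pools on-CPAP change from different starting points in the two arms, so its change over time mixes CPAP with diabetes education and, for A1C, regression to the mean

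*Combined protocol and SAP*

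**What the plan says.** The Analysis Strategy for Aim 4 will "combine the 6 months of data for the two groups receiving CPAP", counting sham participants once they cross over. It aims to explore whether treatment gains are kept and how outcomes relate to CPAP adherence. The Design paragraph gives the pooled data a similar purpose. The time origin is fixed for one arm only: "For delayed treatment group participants, the initial assessment for this analysis will be their assessments at 12 weeks from study start".

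The method is given as "Random coefficient modeling will be applied to model changes in sleep quality, daytime sleepiness, mood, diabetes self-management and glycemic control", linked to recorded adherence. The output is "Estimated regression coefficients and confidence intervals will be reported to summarize changes in outcomes over time and their associations with CPAP adherence". No term for original arm, study week or education is named, and no off-CPAP comparison.

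Three other places matter:

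- Under Procedures, Assessment 1 includes a "venipuncture to obtain no more than 30 cc blood for A1C, fructosamine, and lipid profile". It is the only assessment with a blood draw described before randomisation.
- Eligibility requires "T2DM with suboptimal glucose control", set at A1C of at least 6.5%. The exclusion list removes values above 11.
- Diabetes education and counselling (DEC) is given in both arms in sessions and calls "that will start approximately one week after subjects have started CPAP or sham-CPAP". In support the protocol says "Data from a RCT suggests that 3 1-hr individual sessions results in significantly" lower A1C and less diabetes stress than group sessions. It gives no size.

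The protocol change dated 7.12.2018 gives the sham arm 12 weeks of active CPAP instead of 24 and removes Assessment 5. Aim 4 and its analysis paragraph still speak of 24 weeks on active CPAP.

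**The concern.** Time zero means different things in the two arms. For the active arm it is, by inference, a value taken before education and subject to the A1C limits. For the sham arm it is a value taken after 12 weeks of the same education, with no A1C limit applied at that visit.

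In Aims 1 and 2 this does no harm, because both arms share the selection and the education and the contrast cancels them. Aim 4 names no contrast with untreated time. Anything that moves the active arm after Assessment 1 enters the pooled change as though CPAP had caused it. A fall in A1C could then be reported as a lasting CPAP benefit when education, plus some regression to the mean, produced it.

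**Working it through.** Aim 4 has no sample-size, power or effect figure to reproduce. The check is therefore what the described analysis returns when CPAP does nothing.

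**Inputs from the documents.** Selection on A1C from 6.5 to 11. Equal allocation. On-CPAP visits after the 2018 change: active at weeks 0, 6, 12 and 24; sham at study weeks 12 and 24, which are CPAP weeks 0 and 12.

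**Assumed inputs.** Source-population A1C mean and SD, test-retest correlation r, and education gain. The documents give none of these.

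**Step 1: regression to the mean.** For a normal first value X with mean m, truncated to 6.5-11, the expected fall at a later visit is (1 - r) × (E[X | 6.5 ≤ X ≤ 11] - m). Over m 7.0-7.6, SD 1.3-1.6 and r 0.8-0.9, the extremes are:

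- Smallest (m 7.6, SD 1.3, r 0.9): truncated mean 8.034, so 0.1 × 0.434 = 0.043.
- Largest (m 7.0, SD 1.6, r 0.8): truncated mean 7.941, so 0.2 × 0.941 = 0.188.

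The range is 0.04 to 0.19 points. Wider inputs (m 7.0-8.0, SD 1.2-1.6, r 0.7-0.9) give 0.02 to 0.28.

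**Step 2: pooled slope with no CPAP effect.** Take m 7.5, SD 1.6 and r 0.8. The truncated mean is 8.149, so regression to the mean is 0.2 × 0.649 = 0.13. Let education lower A1C by 0.3 points, building evenly to week 12 and then holding. Mean A1C relative to Assessment 1 is then:

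| CPAP week | 0 | 6 | 12 | 24 |
|---|---|---|---|---|
| Active | 0 | -0.28 | -0.43 | -0.43 |
| Sham after the switch | -0.43 | - | -0.43 | - |

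Here -0.28 = -(0.13 + 0.15) and -0.43 = -(0.13 + 0.30). One linear slope fitted to both rows with a random intercept, a simplification of the planned model, gives -0.31 points per 24 weeks. Simulation with 4,000 per arm and 12 repeats agrees: -0.3075 (Monte Carlo SE 0.003). By arm, the true change is -0.43 in the active arm over weeks 0 to 24, zero in the active arm over weeks 12 to 24, and zero in the sham arm. With 84 per arm the slope's standard error is about 0.10, and about 90% of simulated trials were nominally significant at .05.

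**Step 3: sensitivity** (m 7.5, SD 1.6, r 0.8-0.9, no CPAP effect).

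| Education gain | Pooled slope per 24 weeks |
|---|---|
| 0 | -0.03 to -0.08 |
| 0.3 | -0.27 to -0.30 |
| 0.5 | -0.42 to -0.46 |

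These come from single large simulated samples, so -0.30 here and -0.31 above are the same result. With the week-36 visit restored, the 0.3-point case gives -0.17 to -0.20. The 2018 change therefore enlarges the problem: CPAP weeks 12 to 24 now come from the active arm alone.

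**Step 4: adherence association** (0.3-point gain, r 0.8). The adherence-by-time coefficient, per nightly hour and 24 weeks, is 0.001 (Monte Carlo SE 0.002) when adherence is unrelated to arm. It is -0.026 (Monte Carlo SE 0.002) when mean adherence differs by 1 hour between arms.

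**Step 5: with a control.** Keeping the sham arm's weeks 0 to 12 as off-CPAP time and adding categorical study week moves the CPAP-time slope to +0.015 per 24 weeks (Monte Carlo SE 0.008), close to the true zero.

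**The case against.** Aim 4 is labelled exploratory, with no hypothesis or power claim, and its main object is the association with adherence. Step 4 shows that association essentially unbiased when adherence is unrelated to arm. This stands and limits the point to the reported change over time, unless adherence differs by arm or tracks education uptake.

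The active arm's origin, and the use of one A1C sample for both eligibility and baseline, are inferred. That also stands. The inference is strong because no other pre-CPAP assessment is described, but the text should state it.

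The Aim 4 paragraph is a short description rather than a model equation, and the Preliminary Analyses text allows covariates secondarily. So the accurate statement is that no term is named, not that one is ruled out. The general covariate wording does not address unequal time origins.

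A reader might infer that retention cannot be learned from these data at all. The documents do not support that: time is not said to be linear, and the active arm has both week 12 and week 24 visits. A reader might also infer that education acts in one arm's window only. That is too clean. The protocol says A1C reflects 2 to 3 months, and step goals rise through the 12 weeks, so some gain may reach the sham arm's CPAP period. Lastly, regression to the mean from A1C selection acts directly on A1C and on other outcomes only through their correlation with it.

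**Conclusion.** The point holds for the pooled change over time. As described, it cannot separate CPAP from education and, for A1C, from regression to the mean. Under the assumed inputs, regression to the mean contributes 0.04 to 0.19 points. An assumed 0.3-point education gain with no CPAP effect yields about -0.31 points per 24 weeks. Education is the larger part at that gain and may also move the self-management outcomes. These sizes illustrate the mechanism and do not predict the result.

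It would be wrong to conclude that the adherence analysis is invalid or that the trial's main results are biased. The first depends on conditions that the documents do not settle. The second does not follow, since Aims 1 and 2 compare randomised arms with the same selection and education. The change is worth making because Aim 4 is meant to speak to lasting treatment effects, and the paragraph already needs revision after the 2018 change.

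**What to change.** Revise the Aim 4 paragraph as follows:

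1. State the active arm's time origin and which A1C sample serves as eligibility value and baseline.
2. Keep the sham arm's weeks 0 to 12 in the model as off-CPAP control, with study week as a categorical factor.
3. Add original arm and arm by CPAP-time, in the adherence model too, and report on-CPAP change by arm. The interaction should be with time on CPAP: two arms at four visits give 8 cell means, and a full arm-by-study-week interaction uses all 8, leaving none for CPAP time.
4. Estimate retention as the active arm's change from week 12 to 24, using a simple change contrast or a random-intercept model. Two visits give three variance-covariance elements, too few for the four parameters of a random intercept, random slope, their covariance and a residual.
5. Call the sham arm's change after the switch initial response, and label any pooled change as uncontrolled.
6. Reconcile Aim 4 and its analysis paragraph (24 weeks on active CPAP in everyone) with the 7.12.2018 change (12 weeks for the sham arm, no Assessment 5).

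The cost is SAP text and wider intervals than the pooled slope gives. No new data are needed. One limit remains: after week 12 no group is off CPAP by design, so the week 12 to 24 change is free of the selected starting value but still has no concurrent control.

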## D. PROTECTION of HUMAN SUBJECTS

### Risks to the Subjects

#### Human Subjects Involvement and Characteristics.

The study sample will be 210 individuals with T2DM recruited from the community or the VAPHS with suspected OSA. Verbal consent will be requested from the potential participants prior to the telephone screening. The telephone screening will use a script to query for inclusion and exclusion criteria. The PI or Project Manager/ Study Coordinator will obtain written informed consent for each study subject at Assessment 1. No study related procedure will be done prior to consenting and giving the subject ample opportunity to ask any questions he/she might have. The clinical protocol has been developed with the focus on maintaining safety and scientific integrity. Potential CPAP/sham-CPAP subjects will be evaluated by a physician or nurse practitioner (not one of the study investigators) to determine that the individual is a safe and appropriate subject for the study. Throughout the data collection period of this protocol we will assess for any adverse events associated with CPAP/sham-CPAP treatment.

Inclusion criteria. Subjects in the final sample who are randomized to CPAP or sham-CPAP will have suboptimal diabetes management (A1C  $\geq$  6.5%), AHI greater than  $\geq$  10 (ApneaLinkPlus®); age 18 years and older, and willing to be randomized to CPAP or sham-CPAP.

Exclusion criteria. The exclusion criteria are intended to enhance subjects' safety and ability to complete the study protocol. The table (Table 3) explains the rationale for these exclusions.

**Table 3: Rationale for Exclusion Criteria**

Exclusion Criteria	Rationale
A1C $\geq$ 11.0%	These individuals may need changes in diabetes medications
Type 1 or gestational DM	Etiology not associated as directly with OSA as T2DM
Sleep duration $<$ 4 hrs per day	Inadequate sleep may be confounding barrier in addition to OSA
Diabetes meds: change in oral medications or $>$ 10% change in insulin in last 3 months	Improvement in diabetes control from med change may confound results
Acute medical or surgical conditions or hospitalization $\leq$ 3 months (such as angina, stroke, major surgery, major depression or serious psychiatric conditions)	Subject may be unstable and inappropriate for clinical trial
Previous Dx. of another sleep disorder	Additional sleep disorders may result in continued sleep disturbance
Oxygen or bi-level PAP required	Unable to randomize to sham-CPAP
O2 sat. $<$ 75% for $>$ 25% of the Dx. PSG	Significant hypoxia presents a danger to delay treatment
Prior CPAP or persons in household with CPAP	Increased difficulty in maintaining blinding to CPAP vs sham-CPAP
Cardiovascular events noted during overnight titration sleep study	Significant cardiovascular events presents a danger to delay treatment
Hx. of near-miss or auto accident during last 12 months	Danger of accident from sleepiness
Employed in safety sensitive job (i.e. truck driver or airline pilot)	Danger of accident from sleepiness
Non-ambulatory	Physical activity with walking is aim of study
Regular use of hypnotic or alerting (e. g. modafinil) medications	May interfere with nighttime sleep or daytime alertness
Consumption of alcohol: Men: <math>></math> 4 drinks a day and more than 14 drinks per week Women: <math>></math> 3 drinks a day and <math>></math> 7 drinks per week	May interfere with nighttime sleep or daytime alertness
Claustrophobia to wearing mask	Potentially unable to wear CPAP mask
Unable to speak, read & write English	Not able to perform study tests and participate in the DEC sessions
Pregnant or intend to become pregnant in the next four months (postmenopausal or confirmed not pregnant by a urine pregnancy test)	Changes in respiration, sleep, and energy potentially confound the results
Primary Care Provider request	Subject may be unstable or otherwise inappropriate for clinical trial

#### Sources of Materials.

All data will be collected solely for the purpose of this study. We will collect the following data for research purposes: Trained staff will perform anthropometric measures, calculate BMI, and obtain blood (venipuncture) to be assayed for A1C, fructosamine, and lipid profile levels for all subjects. We will ask for urine specimens to determine pregnancy in potentially pregnant subjects. We will gauge physical activity and sleep quality/quantity from the SenseWear Armbands® and Sleep/Activity diaries and determine adherence to CPAP from a wireless EncoreAnywhere™ device in the CPAP/sham-CPAP devices that are uploaded to a secure server. Subjects will be told that their adherence to CPAP is being monitored with the devices. We will record vigilance information from the PVT-B and questionnaires that elicit data regarding sleep, sleepiness and mood. We will record the results of the ApneaLinkPlus™ and the overnight PSG that

measures sleep variables including the AHI. We will obtain information from the titration study that records the optimal pressure limit to alleviate episodes of apnea and hypopnea.

Data will be identified only by subjects' assigned unique number and will be stored in locked filing cabinets accessible only to investigators and project staff.

#### Potential Risks

There are a few potential risks to the proposed protocol. The procedures and standardized tests required by this protocol are all standard assessment techniques that are widely used on patients. The standardized tests employed in the project pose minimal risk to subjects. We will also take precautions to ensure that no patient who is sleepy is permitted to drive home at the end of an assessment visit. Participants will be informed of the danger of driving while sleepy and asked not to drive when experiencing sleepiness. Subjects will be informed that their use of CPAP will be monitored. Except for untreated daytime sleepiness, there are no known risks to the application of the sham-CPAP. As described above, there is no hazard of CO2 retention or exacerbation of nocturnal symptoms including respiratory events. This placebo has been used in previous research without any serious adverse incident (personal interview [name], APPLES PI, May 29, 2008) and data from the CATNAP ([name], Consultant) trial indicates minimal risk to study participants. Subjects will experience side effects associated with the technological interface as they would with active CPAP treatment.

Our consideration of the ethical issues related to the use of the placebo is addressed in that subjects are fully informed that they may be on a sham-device during the consent process. The sleep evaluation and treatment of subjects will be according to clinical guidelines with the exception of subjects treated with the sham-CPAP intervention. Subjects who are assigned to the sham-CPAP will be given the opportunity to participate in a therapeutic use of CPAP at the completion of their study. Subjects may feel boredom or stress in filling out questionnaires and may view study requirements as burdensome. Subjects may have bleeding, bruising, soreness (infrequent; occurs in 1%-10% of people) and fainting or infection at the site of venipuncture (rare; occurs in less than 1%). The *ApneaLink* Plus risks include the potential for the subject to experience nasal mucosa irritation from the cannula (common, occurs in 1-25%) or skin irritation around the nose and or behind the ears from the nasal cannula (rare, occurs in less than 1%). There are no risks associated with becoming entangled in the breathing tube during sleep. The breathing tube is short (21 inches in length) from the recording device to the nose. Mild skin irritation at the site of the finger sensor, similar to what one might experience when taking a bandage off is rare (occurs in less than 1%).

The BodyMedia SenseWear Armband® activity monitor is powered by a rechargeable battery; the chance of a mild electrical shock is very unlikely. The monitor fits around the upper arm and is secured with Velcro. There is the unlikely possibility of a rash or chafing at the site under the armband.

#### Recruitment and Informed Consent

A record without any identifiers will be kept of all individuals who contacted the study but refused to participate. Individuals not consenting to participate will be asked for the reason for their decision. This reason will be documented in the tracking system. We will read them a statement asking for voluntary oral permission to participate in the telephone screening process. Respondents who do not want to participate in the screening will be thanked and no further questions asked. The questions asked in this screening interview pose no more than minimal risk for the potential participants and are questions that would not require prior consent outside the research context. Those who meet preliminary eligibility criteria will be invited to enroll in the study. Recruitment will be monitored monthly (see Table 4). We will utilize the expertise of Drs. [name] and the involvement of the entire research team of investigators and staff in achieving our recruitment goals.

